9.2 Planned number of the study subjects

In the studies of the drug Adept[®] (Innoventica plc), maximally close to the test drug by mechanism of action, a primary endpoint was used. It was determined as a decrease in number of adhesions during second look diagnostic laparoscopy by 3 or more (in patients with 10 or less adhesions at the baseline) or by 30% and more (in patients with >10 adhesions at the baseline) is 45%.

Performance of second look laparoscopy under the present study is unacceptable from the ethical point of view, MRI will be used for evaluation of the primary end point. As per the publication (21), MRI data highly correlate with laparoscopy picture (both pre-surgical and post-surgical studies during repeated laparoscopies). The exclusions are the thinnest adhesions that may not be seen on MRI which may be compensated by use of high-field MRI. Hence, MRI allows to visualize adhesions qualitatively and quantitatively and to obtain data with the same degree of detalization as during laparoscopic investigation before and after the surgery.

Thus, calculation of sample size will be based on efficacy of similar drugs studied based on laparoscopic data, however, MRI control will be used in the study, first of all due to ethical considerations and due to strong correlation between MRI data and laparoscopy data.

Accordingly, as per the above studies of the drug Adept[®] (20), efficacy related to achieving the primary end point (clinical efficacy determined as a decrease in number of adhesions during second look diagnostic laparoscopy by 3 and more (in female patients with 10 or less adhesions at

the baseline) or by 30% and more (in patients with > 10 adhesions at the baseline)) is 45%. In the control group (placebo) based on literature review and meta-analysis (31) achieving clinical efficacy is recorded in not more than 10% cases.

Using these baseline data, the following assumptions were introduced (as per the method specified in (32)):

- The study will be conducted as a *superiority trial*, i.e. at least one dosage of Seroguard must be more efficient than the placebo, whereby the *superiority margin* will be 5% and more (definition of endpoint and superiority margin from the main study of Adept® was used). Comparison with placebo will be performed for each dosage of the drug separately. Comparison of dosages by efficacy between them is not planned and will be a subject of investigation in the Phase III of clinical studies of the drug
- Expected rates of achieving the primary endpoint in the groups with different dosages will be considered initially equal
- First type error (α) = 5 % (0.05) for *superiority* hypothesis
- Second type error (β) = 20 % (0.2), that corresponds to 80 % power.
- Expected withdrawal from the study will make 15% at screening and 10% after randomization

Null and alternative hypotheses for the *superiority testing* stage are worded as follows:

1. Null hypothesis (H_0) holds that the difference in the rate of the primary endpoint achievement for one of the dosages of the drug Seroguard and the placebo will not exceed 5% in favor of the drug

$$H_0: p_1 - p_0 \leq 0.05$$

2. Alternative hypothesis (H_A) holds that the difference in the rate of the primary endpoint achievement of one of the dosages of the drug Seroguard and the placebo will exceed 5% in favor of the drug

$$H_A: p_1 - p_0 > 0.05$$

Where p_0 and p_1 are the rates of the primary endpoint achievement in the groups of the placebo and Seroguard (of any dosage), respectively.

For the purpose of calculation of the sample size in each group in this case, the formula is applied which is given in (33)

$$n = (p_1 \times (1 - p_0) + p_0 \times (1 - p_0)) \times \left(\frac{z_{1-\alpha} + z_{1-\beta}}{p_1 - p_0 - \delta} \right)^2$$

where

n is the size of one group;

z is the value of the normal distribution function with the given α and β levels;

δ is superiority margin - 5%;

p_1 is the expected percentage in the active drug group (one of the dosages) – 45%

p_0 is the expected percentage in the placebo group – 5%

Applying the above data into this formula, we obtain the minimum number of patients in the placebo group without considering withdrawal: 24 completed cases which corresponds to 26 randomizations and 30 screenings.

Thus, the total number to be enrolled in the study is:

- 1) Placebo group, 1.5 mL/kg – up to 30 screened female patients that corresponds to 26 randomizations and 24 completed cases
- 2) Placebo group, 2.4 mL/kg – up to 30 screened female patients that corresponds to 26 randomizations and 24 completed cases
- 3) Seroguard group, 1.5 mL/kg – up to 30 screened female patients that corresponds to 26 randomizations and 24 completed cases
- 4) Seroguard group, 2.4 mL/kg – up to 30 screened female patients that corresponds to 26 randomizations and 24 completed cases

Thus, total of 120 female patients are to be screened and at least 104 female patients are to be randomized for the study.

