9.1.2 Analysis of main efficacy parameters

Main efficacy parameter in the given study is achieving clinical efficacy of the drug defined as:

- Frequency of reducing number of adhesions after repeated MRI by 3 or more (in female patients with 10 and less adhesions at the baseline) or by 30% and more (in patients with >10 adhesions at the baseline)) in comparison to baseline MRI data

Considering that the given analysis will be performed in the confirmation form of superiority over placebo hypothesis (superiority testing), unilateral statistical criteria will be used, and the level of significance will be established at 5%. For differences between each dose of the drug Seroguard and the placebo, a bilateral 95% binominal accurate confidence interval will be calculated for percentage difference. Superiority will be confirmed, if the lower limit of the confidence interval will exceed 0.05 (5%).

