9.3 A significance level used

In all the tests, a 5% significance level will be used, whereby a primary endpoint will be analyzed using unilateral test, and bilateral statistical tests will be used for analysis of secondary endpoints.

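### The primary test is given two conflicting levels, one-sided 5% and a two-sided 95% interval; at a 10% placebo rate neither delivers both a 5% either-dose error and 80% power per dose

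*Protocol*

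**What the plan says.** Section 9.2 defines success as a claim that either dose can deliver: "at least one dosage of Seroguard must be more efficient than the placebo". It adds: "Comparison with placebo will be performed for each dosage of the drug separately". It sets "First type error (α) = 5 % (0.05) for" the superiority hypothesis, and "Second type error (β) = 20 % (0.2), that corresponds to 80 % power". The sample-size formula uses z at 1−α, so that 5% is one-sided. The synopsis repeats these statements.

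Section 9.3 agrees: "In all the tests, a 5% significance level will be used, whereby a primary endpoint will be analyzed using unilateral test".

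Section 9.1.2 opens in the same way: "unilateral statistical criteria will be used, and the level of significance will be established at 5" per cent. It then says that, for each dose, "a bilateral 95% binominal accurate confidence interval will be calculated for percentage difference", and gives the decision rule: "Superiority will be confirmed, if the lower limit of the confidence interval will exceed 0.05 (5"%).

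Two inputs are also unsettled. The synopsis takes a placebo response of 10%, and the narrative in 9.2 says not above 10%, but the formula inputs in 9.2 list 5%. There are two placebo arms, one per volume, and the protocol does not say whether a dose is compared with its own-volume arm or with both arms pooled.

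**The concern.** A one-sided test at 5% corresponds to the lower limit of a two-sided 90% interval. The lower limit of a two-sided 95% interval is a one-sided test at 2.5%. Section 9.1.2 asks for both, and 9.2 and 9.3 side with the first. A result with a one-sided p-value between 2.5% and 5% would be a success under one sentence and a failure under the next.

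The conflict matters more here because there are two chances to win. The level per dose decides whether the overall chance of a false claim stays near the declared 5% or comes close to twice that. It also decides whether the declared 80% power is real. Section 9.1.2 describes the analysis as confirmatory, so the rule should be unambiguous before unblinding.

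**Working it through.** **Inputs.** Response 45% on active drug; placebo p0 = 10% (synopsis) or 5% (9.2 formula inputs); margin δ = 5 points; 24 completers per arm; two dose comparisons. z values: 1.645 (one-sided 5%), 1.960 (one-sided 2.5%), 0.842 (80% power).

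**1. Reproduce the plan's 24.** With the usual variance term, n = [p1(1−p1) + p0(1−p0)] × ((z₁₋α + z₁₋β)/(p1 − p0 − δ))².
- One-sided 5%, p0 = 10%: (0.2475 + 0.0900) × (2.486/0.30)² = 23.18, rounded up to 24. This is the stated figure.
- One-sided 2.5%, p0 = 10%: 0.3375 × (2.802/0.30)² = 29.43, rounded up to 30.

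The formula as printed has p1(1−p0) in place of p1(1−p1). It gives 34.0 at p0 = 10%, and 23.97 (again 24) at p0 = 5%. Both routes to 24 use one-sided 5%; at 2.5% they give 30 and 31. The sizing level is therefore not in doubt.

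**2. Chance that at least one dose falsely succeeds.** This is taken at the edge of the null for both doses (true difference exactly 5 points), where it is largest. With own placebo arms the two comparisons are independent, so it is 1 − (1 − a)². With a pooled placebo of 48, the two statistics share (1/48)/(1/24 + 1/48) = 1/3 of their variance, and a bivariate normal with correlation 1/3 applies.

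| Level per dose (one-sided) | Own placebo arm | Pooled placebo |
|---|---|---|
| 5% | 1 − 0.95² = 9.75% | 9.2% |
| 2.5% | 1 − 0.975² = 4.94% | 4.7% |

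**3. Power per dose with 24 against 24.** Power = Φ((p1 − p0 − δ)/SE − z₁₋α), with SE = √([p1(1−p1) + p0(1−p0)]/24).
- p0 = 10%: SE = √(0.3375/24) = 0.1186 and 0.30/0.1186 = 2.530.
- p0 = 5%: SE = √(0.2950/24) = 0.1109 and 0.35/0.1109 = 3.157.

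| p0 | One-sided 5% | One-sided 2.5% |
|---|---|---|
| 10% | 81.2% | 71.6% |
| 5% | 93.5% | 88.4% |

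**4. Power to win on at least one dose.** At one-sided 2.5%, with both doses at 45%, p0 = 10% and own placebo arms: 1 − (1 − 0.716)² = 91.9%. With pooled placebo, SE = √(0.2475/24 + 0.0900/48) = 0.1104. That gives 77.6% per dose, and 93.5% for at least one.

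All these figures are nominal normal approximations. Section 9.1.2 asks for an exact interval without naming the method, and an exact method may lower power somewhat: one score-based unconditional version gives about 68% per dose and 90% for either dose at p0 = 10%.

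**The case against.** A reader might infer that the trial simply runs at a 9.75% false-success rate. The documents do not support that as an unconditional statement. The only explicit confirmation rule is the interval rule in 9.1.2. Applied as written, it tests each dose at one-sided 2.5% and keeps the either-dose error at about 4.9%, inside the declared 5%. This objection stands, and it makes the 9.75% conditional on which sentence governs.

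A reader might also fault the protocol for naming no multiplicity procedure. That is weak on its own: section 9.1 leaves the complete analysis to the statistical analysis plan, where such a procedure commonly sits. The point here is a contradiction between rules that the protocol has already fixed.

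The 5% can also be read as applying to each comparison, since the hypotheses in 9.2 are worded for one of the doses. On that reading one-sided 5% per dose is what was promised. It still clashes with the interval rule, and it leaves the either-dose claim with an error of about 9% to 10%.

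Finally, the 72% power depends on p0 = 10%. At the 5% placebo rate listed in 9.2, the interval rule leaves 88% power per dose, so there would be no shortfall. This also stands, and is why the placebo rate has to be settled together with the level.

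**Conclusion.** The firm defect is that 9.1.2 contradicts itself, and that its interval rule also contradicts 9.2, 9.3 and the sample-size calculation. The consequence depends on which statement governs:

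- One-sided 5% per dose: nominal power is 81% at p0 = 10%, in line with the stated 80%, but a false success on at least one dose has a chance of about 9% to 10%.
- The 95% interval rule: the either-dose error is about 4.9%, but power per dose is about 72%.

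At p0 = 10%, no reading gives both a 5% either-dose error and 80% power per dose. The conclusion rests on 24 completers per arm, 45% response on active drug, a 5-point margin and normal approximations. The error rates are worst cases at the edge of the null. The contradiction itself rests on none of these assumptions.

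**What to change.** In 9.1.2, 9.2, 9.3 and the synopsis, state that each dose is tested at one-sided 2.5%, equivalent to the 95% interval rule already in 9.1.2, and delete the one-sided 5% wording for the primary endpoint. Editing only 9.2 and 9.3 would leave the contradiction inside 9.1.2.

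Holm across the two doses is an alternative: the smaller p-value at one-sided 2.5% and, if that succeeds, the other at one-sided 5%. The interval rule would then have to change for the second dose, because one-sided 5% matches a 90% interval.

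In the same edit, say whether the comparator is the volume-matched or the pooled placebo, and reconcile the placebo rate. Then restate nominal power with its assumptions. For separate placebo arms and one-sided 2.5% per dose:
- p0 = 10%: about 72% per dose, and about 92% for at least one dose if both respond at 45%.
- p0 = 5%: about 88% per dose.

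The cost is wording and a less favourable power figure: at p0 = 10% the stated per-dose power falls below 80%. No extra patients are needed if that figure is restated. Keeping 80% for each dose at p0 = 10% would take 30 completers per arm instead of 24.

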	
drug Seroguard and the placebo will exceed 5% in favor of the drug
 $H_A: p_1 - p_0 > 0.05$ 
Where p_0 and p_1 are the rates of the primary endpoint achievement in the groups of the placebo and Seroguard (of any dosage), respectively.
 
For the purpose of calculation of the sample size in each group in this case, the formula is applied which is given in Chow S, Shao J, Wang H. 2008. Sample Size Calculations in Clinical Research. 2nd Ed. Chapman & Hall/CRC Biostatistics Series. page 90
 $n = (p_1 \times (1 - p_0) + p_0 \times (1 - p_0)) \times \left(\frac{z_{1-\alpha} + z_{1-\beta}}{p_1 - p_0 - \delta} \right)^2$ 
where
 
n is the size of one group;
 
z is the value of the normal distribution function with the given α and β levels;
 
δ is superiority margin 5%;
 
p_1 is the expected proportion in the active drug group (one of the dosages) – 45%
 
p_0 is the expected proportion in the placebo group – 10%
 
Applying the above data in this formula, we obtain the minimum number of patients in the placebo group without considering withdrawal: 24 completed cases which corresponds to 26 randomizations and 30 screenings.
 
Thus, the total number to be enrolled in the study is:
 
 1) Placebo group, 1.5 mL/kg – up to 30 screened female patients that corresponds to 26 randomizations and 24 completed cases 2) Placebo group, 2.4 mL/kg – up to 30 screened female patients that corresponds to 26 randomizations and 24 completed cases 3) Seroguard group, 1.5 mL/kg – up to 30 screened female patients that corresponds to 26 randomizations and 24 completed cases 4) Seroguard group, 2.4 mL/kg – up to 30 screened female patients that corresponds to 26 randomizations and 24 completed cases
--	---

	Thus, total of 120 female patients are to be screened and at least 104 female patients are to be randomized for the study.
--	--

Acronyms

ALT	Alanine Aminotransferase
Ap	Alkaline Phosphatase
APTT	Activated Partial Thromboplastin Time
AR	Adverse Reaction
ASA	American Association of Anaesthetists
AST	Aspartate Aminotransferase
ATC	Anatomical Therapeutic Chemical Classification System
BP	Blood Pressure
CI	Confidence Interval
CRF	Case Report Form
CRO	Contract Research Organization
DP	Drug Product
ECG	Electrocardiography
ESR	Erythrocyte Sedimentation Rate
FDA	Food and Drug Administration
FL	Federal Law
GCP	Good Clinical Practice
GGTP	Gamma-Glutamyl Transpeptidase

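### The sample-size calculation uses two placebo rates (10% in the synopsis, 5% in section 9.2) and a wrong variance term, and its 80% power does not match the confidence-interval rule

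*Protocol*

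**What the plan says.** The sample size is justified in two places, the synopsis (statistical analysis row) and section 9.2. Both use a 45% response rate on Seroguard, a 5-point superiority margin, a 5% type I error and 80% power. Both print the same formula, with variance term p1(1−p0) + p0(1−p0) and the quantile z at 1−α. Both arrive at the same answer; in section 9.2 it is "the minimum number of patients in the placebo group without considering withdrawal: 24 completed cases", which is carried forward to 26 randomised per group.

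The placebo rate entered into the formula differs. In the synopsis it "is the expected proportion in the placebo group – 10" per cent. In section 9.2 it "is the expected percentage in the placebo group – 5" per cent. The supporting text in section 9.2 says that on placebo "achieving clinical efficacy is recorded in not more than 10% cases", and the synopsis gives the same bound.

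On the test, section 9.3 says that "a primary endpoint will be analyzed using unilateral test" at the 5% level, and section 9.1.2 also calls for one-sided criteria at 5%. But section 9.1.2 goes on to say that "a bilateral 95% binominal accurate confidence interval will be calculated for percentage difference", and it confirms superiority only if the lower limit of that interval is above 5%. Section 9.2 states that "Comparison with placebo will be performed for each dosage of the drug separately".

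**The concern.** One formula cannot return 24 from both a 10% and a 5% placebo rate when every other input is the same. The planned difference is 35 points in the synopsis and 40 points in section 9.2, and the supporting text, which only gives an upper bound, allows either.

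The printed variance is not that of a difference between two independent proportions. Each arm contributes its own p(1−p), but the first printed term multiplies the active rate by the placebo non-response rate. Repairing only one of the two faults does not restore a consistent derivation: correcting the formula alone leaves section 9.2 at 15, and setting the placebo rate to 10% everywhere while keeping the formula leaves both places at 35.

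The stated 80% is the power of a one-sided 5% test. If success is declared by the interval rule in section 9.1.2, the effective one-sided level is about 2.5% and the power is lower than the protocol claims.

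**Working it through.** **Inputs** (synopsis and section 9.2): p1 = 0.45; margin δ = 0.05; one-sided α = 0.05; power 0.80; p0 = 0.10 (synopsis) or 0.05 (section 9.2). The squared sum of quantiles is (1.645 + 0.842)² = 6.1826, using unrounded values.

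**Formula as printed:** n = [p1(1−p0) + p0(1−p0)] × 6.1826 / (p1 − p0 − δ)²

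- Section 9.2, p0 = 0.05: (0.4275 + 0.0475) × 6.1826 / 0.35² = 23.97, so 24. This reproduces the stated figure.
- Synopsis, p0 = 0.10: (0.405 + 0.09) × 6.1826 / 0.30² = 34.004, so 35 on rounding up. This does not reproduce 24.

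**Formula with the correct variance:** n = [p1(1−p1) + p0(1−p0)] × 6.1826 / (p1 − p0 − δ)²

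- p0 = 0.10: (0.2475 + 0.09) × 6.1826 / 0.30² = 23.18, so 24.
- p0 = 0.05: (0.2475 + 0.0475) × 6.1826 / 0.35² = 14.89, so 15.

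| Placebo rate | As printed | Correct variance | Protocol states |
|---|---|---|---|
| 10% (synopsis) | 34.00 (35) | 23.18 (24) | 24 |
| 5% (section 9.2) | 23.97 (24) | 14.89 (15) | 24 |

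**Power at 24 against 24, p0 = 0.10.** The normal approximation is Φ(0.30 / √[(0.2475 + 0.09)/24] − z). The standard error is √0.0140625 = 0.1186 and the ratio is 2.530.

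- One-sided 5% (z = 1.645): Φ(0.885) = 81.2%.
- Section 9.1.2 interval rule (z = 1.960): Φ(0.570) = 71.6%.

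An exact unconditional test of p1 − p0 ≤ 0.05, with Farrington–Manning score ordering and size maximised over the nuisance parameter, gives 78.6% at one-sided 5% (attained size 0.0493) and 68.4% at one-sided 2.5% (attained size 0.0247).

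**Size needed under the interval rule, normal approximation:** with (1.960 + 0.842)² = 7.849, p0 = 0.10 gives 0.3375 × 7.849 / 0.09 = 29.43, so 30 per arm.

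**Sensitivity.**

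- At p0 = 0.05 with 24 against 24, the normal approximation under the interval rule gives 88.4%, so the shortfall is specific to the 10% rate.
- If the two placebo arms were pooled (24 against 48, p0 = 0.10), power would be 85.8% (normal) and 86.7% (exact) at one-sided 5%, and 77.6% and 71.4% under the interval rule.

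**The case against.** The strongest reply is that 24 is the right number. The standard formula with the synopsis inputs gives 23.18, so the most likely history is a correct calculation, one misprinted subscript and one wrong entry in section 9.2. That stands. The figure of 35 results from the misprint and is not a size the trial needs, and at one-sided 5% neither placebo rate makes 24 too small. The figure is also fragile: with tabled quantiles 1.645 and 0.84 the printed formula gives 0.495 × 2.485² / 0.09 = 33.96, so 34. Either way it is far from 24.

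It can also be said that the equation was read from a PDF and the subscript may be a reading error. The same subscript appears in two separate places, which makes that unlikely, and the conflict over the placebo rate is in plain text and does not depend on it.

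Finally, the power under the interval rule depends on the exact method, which section 9.1.2 does not name and which may properly be left to the analysis plan. This is fair as to the precise figure: ordering by the raw difference instead of the score statistic gives about 49% at 24 against 24. An exact interval inverted from a single two-sided test is also not strictly a one-sided 2.5% test. But at p0 = 10% with single arms, every method tried under the interval rule falls short of 80%.

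**Conclusion.** The concern holds. The placebo rate is 10% in one derivation and 5% in the other, both print an invalid variance term, and both state 24. Section 9.2 reaches 24 only through the wrong formula; the synopsis has inputs that support 24 but prints a formula that does not give it. With the variance corrected, the size is 24 per arm at 10% and 15 at 5%, so the choice of rate matters.

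The stated 80% power holds approximately for a one-sided 5% test at p0 = 10% (81.2% normal, 78.6% exact). Under the section 9.1.2 interval rule it is 71.6% normal and 68.4% exact. These figures assume true rates of 45% and 10%, a single placebo arm, 24 completers in each group and, for the exact figures, score ordering. The enrolment target itself is not shown to be wrong; its documented basis and its power claim are.

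**What to change.** In the synopsis and in section 9.2:

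1. Print the variance as p1(1−p1) + p0(1−p0).
2. State one placebo rate in both places. A rate of 10% agrees with the synopsis and with the upper bound in the supporting text, is the more cautious choice, and keeps 24 per arm. If the sponsor instead justifies 5%, the figure that follows from the corrected formula is 15, not 24.
3. Beside the sample size, give the power for the decision rule that will be applied. This means saying whether the one-sided 5% test of section 9.3 or the two-sided 95% interval of section 9.1.2 decides, which method the figure uses (normal approximation or exact), and whether the comparison is with one placebo arm or both pooled. For 24 against 24 at a 10% placebo rate, the figures are about 81% (normal) or 79% (exact) for the former, and about 72% or 68% for the latter.

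The cost is a text correction through the amendment route in section 11.2. It adds no patients and no procedures.
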